8.8.6 Physical Examination

Physical examination results (normal/abnormal) and details of abnormalities will be listed.

8.8.7 Condition-specific Safety Variables (Part 1 and Part 2)

The following condition-specific safety variables will be summarized by dose cohort for part 1 or by treatment group for part 2 and overall, and by visit using standard descriptive statistics, changes from baseline will be also summarized:

• Total MAS score, calculated as the sum of scores of all items. The MAS score for each item will be re-assigned as the following:

MAS score	Score used in analysis
0	0
1	1
1+	2
2	3
3	4
4	5

- BPI pain severity measured at "worst", "least", "average", and "now", obtained from eCRF;
- Mean BPI pain interference, calculated as the mean of all completed interference items if at least four of all seven items have been completed on a given administration.

For part 2, change from baseline in Bilateral MAS total scores for Elbow, Wrist, Hamstrings, Quadriceps, Gastrocnemius, and Soleus; mean BPI pain score; or mean BPI pain interference score, to Study Day 169 will be analyzed using the same methodology as that used for the primary efficacy endpoint (sections 8.5.2.1 and 8.5.2.1.1). Same statistical analysis will also be conducted for Study Day 253.

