#### Safety:

Safety will be evaluated similarly for both Parts, through the collection of data from:

- Physical examinations
- Vital signs
- 12-lead electrocardiograms
- Laboratory parameters (hematology, blood chemistry, and urinalysis). Analysis of CSF for protein, cell count, and glucose.
- Treatment-emergent adverse events (TEAEs).
  - TEAEs will be defined as any AE occurring during or after the injection of study drug or placebo.
  - TEAEs will be limited to those events occurring within 28 days after the last visit.

Condition-specific safety outcomes will include adverse changes in:

- ISNCSCI, GRASSP and all of the neurological measures evaluated for efficacy
- Spasticity (Modified Ashworth Scale). A clinician administered examination for spasticity which measures muscle tone. A score of 0-4 is assigned to each muscle group evaluated. Note: Testing will exclude fingers and thumb.
- Pain (BPI). A self-administered questionnaire used to assess the severity of a subject's pain and the impact of this pain on the subject's daily functioning.

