3.2 Safety Variables

The following safety variables will be included for both Part 1 and Part 2:

- Study treatment exposure;
- Treatment-emergent adverse events (TEAEs);
- Clinical laboratory tests including hematology, clinical chemistry, and urinalysis;
- Physical examinations;
- Vital signs;
- 12-lead electrocardiograms (ECGs);
- Condition-specific safety outcomes, including the following:
 - Spasticity. Modified Ashworth Scale (MAS) (Pandyan et al. 1999) is a clinician administered examination for spasticity which measures muscle tone around selected limb joints. The total MAS score will be calculated and summarized for both part 1 and part 2. In addition, for part 2, bilateral total scores for Elbow, Wrist, Hamstrings, Quadriceps, Gastrocnemius, and Soleus will be analyzed to compare between treatment group with control group.
 - Pain. Brief Pain Inventory (BPI) (Cleeland and Ryan 1994) is a selfadministered questionnaire used to assess the severity of a subject's pain and the impact of this pain on the subject's daily functioning. The following scores will be calculated and summarized:
 - BPI pain severity for each of the four severity items ("worst," "least," "average," and "now"). For part 2, mean BPI pain score at Study Day 169 and change from baseline will be analyzed to compare treatment group with control group.
 - BPI pain interference. For part 2, mean BPI pain interference score at Study Day 169 and change from baseline will be analyzed to compare treatment group with control group.

4. Pharmacokinetic variables

- Serum and CSF samples will be collected and analyzed for concentrations of AXER-204 at planned time points following the schedules for Part 1 or Part 2, as described in the protocol.
- Pharmacokinetic (PK) parameters will also be determined (section 8.6.1) using a non-compartmental approach (NCA) for Part 1.

5. Immunogenicity variables

Pre-dose Anti-drug antibody (ADA) serum will be collected for ADA analysis for both Part 1 and Part 2 following the protocol defined schedule. The following immunogenicity variables will be analyzed:

• Anti-drug antibody (ADA) incidence

6. Analysis Population

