6.2 Safety Population (Part 1 and Part 2)

The Safety Population will consist of all subjects treated with at least one dose of study treatment. Safety outcomes will be assessed using the Safety Population. For Part 2, safety outcomes, including the condition-specific safety outcomes as described in section 8.8.7, will be analyzed according to their actual treatment received.

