6.3 Full Analysis Set (Part 1)

The Full Analysis Set (FAS) will consist of all subjects who had at least one dose of study treatment and at least one post-baseline ISNCSCI assessment in Part 1. Efficacy outcomes in Part 1 will be summarized using FAS.

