6.4 Modified Intent to Treat Analysis set (Part 2)

The Modified Intent to Treat (mITT) Analysis Set consist of all Part 2 subjects who were randomized and had at least one dose of study treatment and at least one postbaseline ISNCSCI assessment. Efficacy outcomes for Part 2 will be evaluated using the mITT analysis set. Subjects will be analyzed according to their randomized treatment.

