Descriptive statistics (number of subjects, mean, standard deviation, median, minimum and maximum) will be provided for baseline, post treatment and change from baseline by treatment group and visit.

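### The SAP drops ISNCSCI, GRASSP and the other neurological measures from the protocol's safety outcomes without saying so, and no Part 2 table counts subjects whose motor, sensory or functional scores fell

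*SAP*

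**What the plan says.** **Protocol.** The synopsis safety section states: "Condition-specific safety outcomes will include adverse changes in", and its first item is "ISNCSCI, GRASSP and all of the neurological measures evaluated for efficacy". Spasticity and pain follow as further items. Protocol 14.1 and 15.11 repeat the same item as a condition-specific safety outcome, but without the reference to adverse change. Protocol 15.11 adds that changes in safety endpoints are computed much as for efficacy and that no inferential statistics are given for them.

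**SAP, safety.** Section 3.2 has the heading "Condition-specific safety outcomes, including the following", and only MAS and BPI come under it. Section 8.8.7 begins "The following condition-specific safety variables will be summarized by dose cohort" and names total MAS, BPI severity and BPI interference. Section 6.2 requires that "safety outcomes, including the condition-specific safety outcomes as described in section" 8.8.7 be analysed in Part 2 by treatment actually received.

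**SAP, efficacy.** The neurological scores appear here instead. For Part 1, section 6.3 says "Efficacy outcomes in Part 1 will be summarized using FAS". For Part 2, section 6.4 says "Efficacy outcomes for Part 2 will be evaluated using the mITT analysis set", by randomized arm.

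**SAP, declared changes.** Sections 9.1 to 9.3 cover PGIC, the exploratory endpoints and the analysis sets. They do not say that any measure was taken out of the safety outcomes.

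**The concern.** Safety and tolerability are a primary objective of both parts. The product is given by repeated lumbar puncture and is meant to alter axon growth, so loss of motor or sensory function is a harm a reader would look for first. The protocol treats it as a safety outcome, whereas the SAP's safety chapter has no table for it.

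The contrast with other safety data is plain. SAP 8.8.3 gives laboratory shift tables and counts of subjects with new-onset out-of-range values. SAP 8.8.5 gives ECG shifts to the worst post-baseline reading. Neither kind of display is planned for UEMS, LEMS, the sensory scores, GRASSP, SCIM III or AIS grade. If a few subjects lose function while others gain a little, the safety tables would not show how many lost it.

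**Working it through.** The plan gives no figure to reproduce. The check is a comparison of texts, followed by a small illustration.

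**1. Where each measure goes**

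| Measure | Protocol safety list | SAP 3.2 / 8.8.7 | Part 2 display elsewhere in the SAP |
|---|---|---|---|
| MAS, BPI | yes | yes | – |
| UEMS | yes | no | MMRM, slope, summary statistics (8.5.2.1, 8.5.2.1.1) |
| LEMS | yes | no | only within total motor score (3.1.2.5.1, 9.2) |
| Light touch, pin prick | yes | no | same methods as UEMS (8.5.2.3) |
| GRASSP, SCIM III | yes | no | same methods as UEMS (8.5.2.2, 8.5.2.3) |
| AIS grade | yes | no | counts per visit (8.5.2.3) |
| ISAFSCI | yes | no | shift table to Day 169 (8.5.2.3) |

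I read the protocol's item as covering SCIM III and ISAFSCI because it extends to all neurological measures used for efficacy.

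**2. What the efficacy summary shows.** SAP 8.5.2.1 says: "Descriptive statistics (number of subjects, mean, standard deviation, median, minimum and maximum) will be provided for baseline, post treatment and change from baseline", by arm and visit. Take 16 subjects per arm (Protocol 7.2) and two invented sets of whole-number UEMS changes:

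- Set A: three subjects lose 5, eleven gain 1, two gain 2. Sum = -15 + 11 + 4 = 0, so the mean is 0. SD = √[(75 + 11 + 8)/15] = √6.27 = 2.5. The median is +1 and the minimum -5.
- Set B: one subject loses 5, five gain 1, ten are unchanged. Sum = -5 + 5 = 0, so the mean is 0. SD = √[(25 + 5)/15] = √2 = 1.4. The median is 0 and the minimum -5.

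The mean and minimum agree, yet 3/16 = 19% declined in A and 1/16 = 6% in B. The SD and median differ, but neither converts into a count. One subject losing 5 points moves the arm mean by -5/16 = -0.31, and one losing 10 moves it by -10/16 = -0.63. Both are small beside the SDs in SAP 2.3.2 (3 and 4 for planning, 2.0 observed in Part 1).

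**3. AIS.** If one subject goes from C to D and another from D to C, the counts per visit do not change. A shift table would show both moves.

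**4. LEMS.** SAP 9.2 replaces the lower extremity score with total motor score. SAP 3.1.2.1 itself notes that combining arm and leg scores has not been recommended for a decade. A subject who gains 4 arm points and loses 4 leg points has a total change of 0. An arm's mean LEMS change can be recovered by subtracting mean UEMS from mean total motor score when the same subjects contribute. Its minimum and the number who declined cannot.

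**5. How much noise a count would contain.** Assume no true change and normally distributed differences rounded to whole points. At a single visit, P(any decrease) = Φ(-0.5/SD) and P(decrease of 3 or more) = Φ(-2.5/SD).

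| SD | Any decrease | Expected of 16 | 3 or more | Expected of 16 |
|---|---|---|---|---|
| 2 | 40% | 6.4 | 11% | 1.7 |
| 3 | 43% | 6.9 | 20% | 3.2 |
| 4 | 45% | 7.2 | 27% | 4.3 |

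Worst post-baseline counts would be higher still. The counts therefore carry information only beside the placebo arm.

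**The case against.** The strongest reply is that this is a filing difference. The protocol sets no threshold for decline and asks for no count of subjects who worsened. Protocol 15.11 wants safety changes handled like efficacy changes, and the SAP produces tables of that kind under another title. Minimum and median change, AIS counts, the ISAFSCI shift table, PGIC and CGIC categories that include worsening, and full listings are all planned. Worsening of the underlying disease can be reported as an adverse event, and radicular injury and central nervous system complications are adverse events of special interest (Protocol 14.2.1, 14.2.3).

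Much of this stands, and it rules out three stronger readings that a reader might infer:

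- *That individual decline would be invisible.* It would not. In Set A the planned table shows a minimum of -5 and a median above the mean.
- *That the protocol promised counts of decliners.* It did not. It promised that these measures would be safety outcomes, and only the synopsis speaks of adverse changes. The counts are a proposed way to honour that.
- *That the mITT set hides affected subjects.* It hardly can. A treated subject outside mITT has no post-baseline ISNCSCI, and every GRASSP and SCIM III visit also includes ISNCSCI. Randomized and actual grouping differ only if there is a misallocation.

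The reply does not remove the omission. The wording of SAP 3.2 could be read as open-ended, but section 6.2 points to 8.8.7 for the condition-specific outcomes, and 8.8.7 does not contain these measures. Adverse event reporting depends on investigator judgement, and loss of motor or sensory score is not a named event of special interest. Noise in the counts is a reason to show both arms.

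**Conclusion.** The point holds as an undeclared departure from the protocol with a limited but real reporting gap. Three protocol sections name the neurological measures as safety outcomes, both SAP safety lists omit them, and section 9 is silent. Apart from ISAFSCI, no planned Part 2 display counts subjects whose neurological scores fell or shows who changed AIS grade, and LEMS is not summarized separately. The data remain available through efficacy tables and listings.

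The size cannot be expressed as an effect on power or error rate, since none is involved. The illustration puts it at 6% versus 19% of an arm declining behind the same mean and minimum. It rests on invented changes and 16 per arm. Nothing in the documents indicates that such a decline occurred.

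The 3-point benchmark is the SAP's figure for UEMS in acute and subacute injury. SAP 2.3.2 says none has been determined for chronic injury, and the documents give none for LEMS. It can serve as a descriptive cut, not as a definition of harm. The change should be made because safety is a primary objective and the remedy is cheap.

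**What to change.** Restore the measures to SAP 3.2 and 8.8.7, for the Safety Population by actual treatment, descriptive only.

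- **Part 2**, at each scheduled visit (ISNCSCI at Days 21, 63, 104, 169 and 253; GRASSP and SCIM III from Day 63) and at worst post-baseline:
  - n (%) with any decrease, and with a decrease of 3 points or more, in bilateral UEMS and separately in LEMS, with a footnote on the origin of the 3-point cut;
  - n (%) with a decrease in light touch, pin prick, each GRASSP subscore and the two SCIM III subscores;
  - a shift table of AIS grade from baseline to worst post-baseline.
- **Part 1**: the same at Day 29, by dose cohort.
- **Documentation**: record the omission in section 9. Section 10 shows that this SAP version already contains changes made after the Day 169 results were seen, so label the new tables as added after that unblinding.

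The cost is some SAP wording and a few more tables. No new data, alpha or sample size is needed. The drawback is that counts of any decrease include measurement noise, so each should be shown and read beside placebo.

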8.9 Interim Analysis

No interim analysis will be performed for this study.

9. Changes from the Protocol Specified Statistical Analyses

The following changes from protocol specified statistical analyses are made in this SAP.

9.1 Secondary efficacy endpoint

Patient Global Impression of Change (PGIC) responder rate will be considered secondary efficacy endpoint.

9.2 Exploratory efficacy endpoint

- In SAP, ISNCSCI UEMS for the side with the higher baseline score and the side with the lower baseline score will be analyzed as exploratory efficacy endpoint. If the baseline scores for each side are equal, then the right side will be grouped with the higher baseline UEMS scores for analysis.
- ISNCSCI total motor scores instead of lower extremity motor score are included in SAP as exploratory efficacy endpoints.
- Clinical Global Impression of Change (CGIC) from GRASSP Prehension Performance Video Recordings

9.3 Analysis population

PK Analysis set and ADA analysis set were added in the SAP for analysis for PK and ADA, respectively. In addition, mITT analysis set was added for Part 2 and all Part 2 efficacy analysis will be conducted using mITT analysis set.

10. Changes in the Planned Statistical Analyses

The following changes in the planned statistical analyses indicated below are being made after all enrolled Part 2 patients have completed the 6-month visit, cleaning and unblinding of data, and completion of the 6-month top-line analysis for the primary, secondary and exploratory efficacy endpoints to compare treatment effects from baseline to Study Day 169 and prior to final database lock following 9-month visit or Study Day 253 (as described in section 2.2). The availability of results of this analysis was limited to the unblinded ReNetX staff and **Compare** Biostatistics and Programming team. The changes were requested by the unblinded ReNetX staff after review of results and approved by **Compare** Biostatistics and Programming team.

10.1 Post Hoc Exploratory Analysis for Efficacy Endpoints to Study Day 169

Results from the primary efficacy analysis, based upon a mixed-effects model for repeated measures (MMRM) as described in section 8.5.2.1, showed that there was no statistically significant difference at the two-sided 5% significance level between AXER-204 and Placebo groups in the primary efficacy endpoint. Additionally, the MMRM subgroup exploratory analyses (as described in section 8.5.2.1.3) did not show statistical significant difference between treatment and control groups in the primary endpoint at the unadjusted two-sided 5% significance level, but there is visually a potential trend toward treatment effect in the subgroups AIS grade (B, C, D) and no prior receipt of study drug in Part 1.

Therefore, ReNetX performed exploratory analyses on several endpoints in these subgroups, which suggested that three endpoints had visually a higher change from baseline in AXER-204 group compared to Placebo group, and proposed additional post hoc analyses that may reveal treatment effect for the following efficacy endpoints. Similar to the subgroup analyses (section 8.5.2.1.3), the alpha from the primary efficacy analysis has been used, so no adjustment to the significance level for testing will be made because all these analyses will be considered exploratory. For this reason, no formal conclusions can be drawn from any differences, and p-values will be provided for descriptive purposes only.

- **Primary efficacy endpoint:** Change from baseline in bilateral UEMS to Study Day 169 ranging from 0-50.
- **Secondary efficacy endpoint:** Change from baseline in GRASSP bilateral PP to Study Day 169 ranging from 0-40.
- Exploratory efficacy endpoint: Change from baseline in ISNCSCI bilateral motor score (including both upper and lower extremity for both left and right sides) to Study Day 169 ranging from 0-100.

• Including patients with AIS grade (B, C, D)

An analysis including patients with AIS grade (B, C, D) will be conducted in the mITT Analysis set. The same MMRM method as the primary analysis as described in section 8.5.2.1 will be used. Since subgroup analysis of AIS grade (A vs. B, C, D) on the primary efficacy endpoint have already been performed as part of the planned analysis, analysis will only be done on the secondary and exploratory efficacy endpoints.

• Including patients with no prior recent of study drug in Part 1

An analysis including patients with no prior receipt of study drug in Part 1 will be conducted in the mITT Analysis set. The same MMRM method as the primary analysis as described in section 8.5.2.1 will be used. Since subgroup analysis of prior receipt of study drug in Part 1 (yes vs. no) on the primary efficacy endpoint have already been performed as part of the planned analysis, analysis will only be done on the secondary and exploratory efficacy endpoints.

• Including patients with AIS grade (B, C, D) and no prior receipt of study drug in Part 1

An analysis including patients with AIS grade (B, C, D) and no prior receipt of study drug in Part 1 will be conducted in the mITT Analysis set. The same MMRM method as the primary analysis as described in section 8.5.2.1 will be used.

10.2 Post Hoc Exploratory Analysis for Efficacy Endpoints to Study Day 253

All efficacy endpoints as described in section 10.1 will also be analyzed for Study Day 253 similar to the analysis conducted for Study Day 169 for each corresponding endpoint. All post treatment values up until Study Day 253 will be included in the analysis of treatment effect for Study Day 253. Since no subgroup analyses were performed for Study Day 253 as part of the planned analyses, all three exploratory analyses will be performed on the primary efficacy endpoint as well as the secondary and exploratory efficacy endpoints.

10.3 Clarifications to Pre Hoc Slope Analysis

Clarifications to the secondary efficacy analysis, based upon a random coefficients model that compared the rate of change (slope) in the primary efficacy endpoint as described in section $\underline{8.5.2.1.1}$, was implemented prior to treatment unblinding for the 6-month top-line analysis (as described in section $\underline{2.2}$). The slope will measure rate of change of bilateral UEMS per month instead of per day in the interest of readability. Conversions from day to month will be baseline as Study month 0, Study day 21 as Study month 1, Study day 63 as Study month 2, Study day 104 as Study month 4, Study day 169 as Study month 6, and Study day 253 as Study month 9.

The slope analysis is similar to the MMRM model in the primary efficacy analysis as described in section 8.5.2.1, but will include bilateral UEMS as the dependent variable; treatment, AIS grade (A,B vs C,D) and prior receipt of study drug in Part

CONFIDENTIAL

1 (yes vs. no) as the fixed categorical effects; as well as visit (Study month 0, 1, 2, 4, and 6) and treatment-by-visit interaction as the fixed continuous effects; and subject and subject by visit as the random effects. The unstructured covariance model will be used. In contrast to the primary efficacy analysis in section 8.5.2.1, if the computational algorithm fails to converge, the following will be tested in order, and the first that converges will be used: variance components covariance structure, removing random effect subject by visit and unstructured covariance structure, and removing random effect subject by visit and variance components covariance structure. Reporting and plotting of the model results will follow as described in section 8.5.2.1.1, but excluding overall rate of change in bilateral UEMS and 95% CI.

11. References

Cleeland, C.S. and Ryan, K.M. (1994). Pain assessment: global use of the Brief Pain Inventory. *Ann Acad Med Singap* **23**(2): 129-138.

